#### 11.2.1 Assessment of Severity

The Principal Investigator (or qualified delegate) will assess the severity for each event based on clinical judgement. The intensity of each event recorded in the CRF should be assigned to one of the following categories:

Mild	An event that is easily tolerated by the subject, causing minimal discomfort and not interfering with everyday activities.	
Moderate	An event that is sufficiently discomforting to interfere with normal activities	
Severe	An event which is incapacitating and prevents normal everyday activities	

#### 11.2.2 Assessment of Causality

The Investigator will assess the potential causal relationship of each event, using clinical judgement. Alternative causes, such as natural history of underlying diseases, other risk factors and the temporal relationship of the event to the IMD and/or comparator product will be considered and investigated. The causal relationship to the IMD and/or comparator is to be assessed by the Investigator (or medically qualified delegate) and should be assessed using the following classifications:

Not related	Polationship to the medical device or precedures can be evaluated when
Not related	Relationship to the medical device of procedures can be excluded when.
	
 
the event is not a known side effect of the product category the device belongs to or of similar devices and procedures;
 

	
 
the event has no temporal relationship with the use of the device or the procedures;
 

	
 
the event does not follow a known response pattern to the medical device (if the response pattern is previously known) and is biologically implausible;
 

	
 
the discontinuation of medical device application or the reduction of the level of activation/exposure - when clinically feasible - and reintroduction of its use (or increase of the level of activation/exposure), do not impact on the event;
 

	
 
the event involves a body-site or an organ not expected to be affected by the device or procedure;
 

	
 
the event can be attributed to another cause (for example, an underlying or concurrent illness/ clinical condition, an effect of another device, drug, treatment or other risk factors);
 

	
 
the event does not depend on a false result given by the investigational medical device used for diagnosis, when applicable;
 

	
 
harms to the subject are not clearly due to use error;
 

	In order to establish the non-relatedness, not all the criteria listed above might be met at the same time, depending on the type of device/procedures and the event.

Clinical Investigation Plan: AI5763

W			
Unlikely related	The relationship with the use of the medical device seems not relevant and/or the event can be reasonably explained by another cause, but additional information may be obtained.		
Possibly related	The relationship with the use of the medical device is weak but cannot be ruled out completely. Alternative causes are also possible (for example, an underlying or concurrent illness/ clinical condition or/and an effect of another device, drug or treatment). Cases where relatedness cannot be assessed or no information has been obtained should also be classified as possibly related.		
Probably related	The relationship with the use of the medical device seems relevant and/or the event cannot be reasonably explained by another cause, but additional information may be obtained.		
Definitely related	The event is associated with the medical device or with procedures beyond reasonable doubt when:		
	
 
the event is a known side effect of the product category the device belongs to or of similar devices and procedures;
 
		
	• the event has a temporal relationship with the medical device use/application or procedures;		
	
 
the event involves a body-site or organ that
 
		
	
 
the medical device or procedures are applied to
 
		
	
 
the medical device or procedures have an effect on;
 
		
	
 
the event follows a known response pattern to the medical device (if the response pattern is previously known);
 
		
	
 
the discontinuation of medical device application (or reduction of the level of activation/exposure) and reintroduction of its use (or increase of the level of activation/exposure), impact on the event (when clinically feasible);
 
		
	
 
other possible causes (for example, an underlying or concurrent illness/ clinical condition or/and an effect of another device, drug or treatment) have been adequately ruled out;
 
		
	harm to the subject is due to error in use;		
	
 
the event depends on a false result given by the medical device used for diagnosis, when applicable;
 
		
	In order to establish the relatedness, not all the criteria listed above might be met at the same time, depending on the type of device/procedures and the event.		

#### 11.2.3 Assessment of Seriousness

The Investigator will assess the seriousness of each event according to clinical judgement and the definition provided in section 11.1.3.

#### 11.2.4 Assessment of Expectedness

An event should be considered unanticipated if the nature, severity, or frequency of that event is not consistent with the applicable safety reference information, such as the risk analysis report, hazards analysis, IB, or Product Information/ Instruction For Use (IFU) if the product is approved for marketing.

For this clinical investigation the listed items in Section 8.2 and 8.3 of this CIP and/or the IB are anticipated ADEs.

Anticipated	An adverse device effect (ADE) which by its nature, incidence, severity, or outcome is consistent with the applicable safety reference information (for example, IB, IFU).	
Unanticipated	An adverse device effect (ADE) which by its nature, incidence, severity, or outcor is not consistent with, or has not been identified in the applicable safety referen information (for example, IB, IFU).	

## 11.3 Recording and Handling of Device Deficiencies

Subjects shall be carefully monitored during the clinical investigation and routinely questioned about DDs at investigation visits. Source notes should indicate the evaluation for DDs, even if there are none to report.

The Investigator shall assess if the DD led to an AE or could have led to a serious medical occurrence (serious adverse device effect) if;

1) suitable action had not been taken,

2) intervention had not been made, or,

3) circumstances had been less fortunate

All DDs will be documented in the source notes and the DD page of the CRF.

### 11.4 Reporting Responsibilities

The Investigator is responsible for reporting all AEs and DDs in the CRF.

#### 11.4.1 Investigator Reporting of Serious Adverse Events

All AEs meeting the criteria for an SAE, or DD that could have led to a SADE, must be reported to the Sponsor without delay.

Reporting is achieved through completion of the events details in the Adverse Event page of the electronic Case Report Forms (eCRF).

The Investigator shall always provide an assessment of causality at the time of the initial report, as described in section 11.2.2 'Assessment of Causality'. If data obtained after reporting indicates that the assessment of causality is incorrect, then the SAE form may be appropriately amended, signed, dated, and resubmitted to the Sponsor.

If the Investigator does not have all other information regarding an SAE, he/she will not wait to receive additional information before reporting the event. The reporting forms shall be updated when additional information is received.

The Investigator is responsible for reporting of safety events to their local Ethics Committee (EC) using the applicable report form, in accordance with local regulations.

#### 11.4.2 Sponsor Notification of Events

The Sponsor is responsible for reviewing all safety data to evaluate potential causality and anticipation of all ADEs.

The Sponsor is also responsible for reporting all reportable events according to the requirements and timelines of the regulatory authorities relevant to this clinical investigation, and shall conduct an expedited assessment of all SAEs, unanticipated ADEs, DDs that could have led to a SADE.

CTC: The sponsor is responsible for reporting to the FAMHP (Federal Agency for Medicines and Health Products): [contact], by using the MDCG 2020-10/2 form: (a) any serious adverse event that has a causal relationship with the investigational device, the comparator or the investigation procedure or where such causal relationship is reasonably possible; (b) any device deficiency that might have led to a serious adverse event if appropriate action had not been taken, intervention had not occurred, or circumstances had been less fortunate; and (c) any new findings in relation to any event referred to in points (a) and (b).

Reporting must be: a) for all reportable events which indicate an imminent risk of death, serious injury, or serious illness and that requires prompt remedial action for other patients/subjects, users or other persons or a new finding to it: immediately, but not later than 2 calendar days after awareness by sponsor of a new reportable event or of new information in relation with an already reported event; or b) any other reportable events or a new finding/update to it: immediately, but not later than 7 calendar days following the date of awareness by the sponsor of the new reportable event or of new information in relation of an SAE/SADE would be incomplete, on receipt of additional information the Sponsor must submit a clearly referenced and numbered follow-up report of the event.

Cochlear Melbourne: The sponsor is responsible for reporting serious adverse events (SAE) that occur in Royal Victorian Eye and Ear Hospital participants to the Human Research Ethics Committee as soon as possible and within 72 hours of occurrence. All internal SAEs (occurring in Eye and Ear participants) must be reported to the Eye and Ear HREC as soon as possible and within 72 hours of occurrence. External SAEs (occurring in participants at other sites) must be reported in a prompt manner if the information would reasonably be expected to adversely affect the continued ethical acceptability of the trial. This includes cases where the information would lead the HREC to require a change in the trial protocol or information statement, including changed monitoring (using the Single SAE form). The Sponsor is required to report to the Therapeutic Goods Administration any fatal or life-threatening Australian USADEs, and all other Australian USADEs within 7 and 15 days respectively.

The Safety Monitor for AE/DD assessment and any AE/DD related queries can be contacted via [contact].

## 11.5 Independent Data Monitoring Committee

Given the low residual risk associated with this study (such as no changes to the implant, no significant changes to the stimulation pattern, only minor changes to the sound processor firmware, absence of surgical risk, audiological risk comparable to clinical follow-up), an IDMC will not be established for this study.

## **12 DEVICE ACCOUNTABILITY**

Supply of investigational medical devices will be recorded using tracking forms such as the Sponsor Device Tracking Form (1295388) and Software Tracking Form (1302326). Investigational medical device(s) will be quarantined at the investigational site and clearly labelled to identify exclusively for use in a clinical investigation. Subject level device supply will be tracked using the Individual Subject

Device Accountability Log Form (1295295). At the end of the clinical investigation, all investigational medical devices shall be returned to the Sponsor. In cases where a commercially released product is required to facilitate the functionality of the investigational device, the commercial product shall be registered following the standard product registration process.

Contact information regarding the IMD and/or comparator is provided below.

Name of contact person of the Sponsor:	
Country and time zone:	Belgium (GMT+1)
Phone number:	
Email:	

## **13 DEVIATIONS FROM THE CLINICAL INVESTIGATION PLAN**

The Investigator(s) must not deviate from the CIP, except in case of an emergency to protect the safety and well-being of the subject(s). Such deviations will be documented by the site personnel in the source documentation for the subject and reported to the relevant EC as per institutional requirements and to the Sponsor as soon as possible, within ample time from the date of the emergency.

If there is a deviation from CIP-defined assessments or parts thereof are omitted or completed incorrectly, the deviation will also be documented by the site personnel in the source documentation for the subject. Depending on the type or severity of the deviation the Investigator may be required to notify the EC, particularly if the deviation potentially impacts subject safety, performance of IMD and/or comparator, or data integrity.

All CIP deviations will be documented in the eCRF to enable analysis and reporting by the Sponsor in the Clinical Investigation Report (CIR), or to the relevant regulatory authority(s), if applicable.

Gross misconduct on behalf of an Investigator, such as intentional non-compliance with CIP or GCP requirements or fraud, will result in disqualification of the Principal Investigator and/or Investigational Site from participation in the investigation. Data provided by the Principal Investigator or Investigational Site will be excluded from the per-protocol analysis group.

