#### 7.2.6 Criteria for Subject Withdrawal

Subjects can decide to withdraw from the investigation at any time. The reason for withdrawal should be documented in the subject's source files and the case report form (CRF).

The Investigator or Sponsor may also decide to withdraw a subject from the clinical investigation if it is considered to be in the subject's best interests.

Subject withdrawal may be for any of the following reasons:

- Adverse Event (AE)
- Device Deficiency (DD)
- CIP or GCP deviation
- Subject withdrew consent
- Subject lost to follow-up
- Subject death
- Sponsor decision
- Investigator decision
- Other

If subject withdrawal is due to problems related to the IMD and/or comparator safety or performance, the Investigator shall ask for the subject's permission to continue in safety follow up (i.e., adverse events) until their scheduled End-of-Study visit. Withdrawal from the umbrella investigation will also result in withdrawal from any active sub-study under this umbrella investigation.

If a subject is lost to follow-up, every possible effort must be made by the study site personnel to contact the subject. At least 3 separate attempts taken to contact the subject must be documented.

Participating subjects who are withdrawn/discontinued might be replaced. This will be specified in the sub-study documentation.

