#### Australia:

External site: HEARnet (in collaboration with Royal Victorian Eye and Ear Hospital, East Melbourne)

Internal (Cochlear) site: Cochlear Ltd. Melbourne.

The principal investigators of the external sites are responsible for subject recruitment, obtaining Informed Consent, assessment of inclusion and exclusion criteria and assessment of hearing and medical history related to this umbrella Clinical Investigation Plan. Subjects may then be referred to the sponsor principal investigator of internal (Cochlear) sites, who will conduct the remaining study procedures as described in the umbrella and sub-study Clinical Investigation Plan. Section 10 describes the Informed Consent process.

The following scenarios for sub-studies are distinguished:

- The sponsor principal investigator or study staff of internal (Cochlear) sites will conduct study procedures at the facilities of internal (Cochlear) sites. The conduct of the study procedures is the responsibility of the sponsor principal investigator.
- The sponsor principal investigator or study staff of internal (Cochlear) sites will conduct study procedures at the facilities of the site of the external principal investigator. The conduct of these study procedures remains the responsibility of the sponsor principal investigator of internal (Cochlear) sites.
- The external principal investigator or study staff of external site(s) will conduct study procedures at the facilities of the site of the external principal investigator. The conduct of the study procedures is the responsibility of the external principal investigator.
- The external principal investigator or study staff of the external principal investigator will conduct study procedures at the facilities of internal (Cochlear) sites. The conduct of these study procedures remains the responsibility of the external principal investigator.

For all scenarios, the coordinating investigator of the sub-study is the coordinating investigator of the umbrella investigation. Study staff (e.g. technical expert) of the external site(s) of the umbrella study may conduct study procedures for which the sponsor principal investigator of a sub-study is responsible, only in case the study staff have the qualification and competence to conduct these study procedures. The conduct of these study procedures is the responsibility of the sponsor principal investigator.

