## 7.6 Sponsor Role in Conduct of the Clinical Investigation

As mentioned in section 7.3, the sponsor principal investigator of the internal (Cochlear) sites may conduct study procedures upon referral of subjects from the external principal investigator. Section 10 describes the Informed Consent process. The procedures performed by the sponsor principal investigator will be clearly described in the sub-study documentation.

There is no mitigation for potential bias to the data integrity. Where possible, a sub-study will be blinded.

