## **9 STATISTICAL CONSIDERATIONS**

### 9.1 General Considerations

Data will be analysed separately per sub-study. Analysis of the data will take place at Cochlear. Substudy specific endpoints and other statistical considerations such as hypothesis and sample size

determination will be described in the sub-study documentation and a sub-study CIR will be written when these endpoints are reached.

Clinical Investigation Plan |

Approval Date (GMT+

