## 9.5 Analysis Populations

A detailed description of the statistical analysis that will be used for each sub-study will be described in the sub-study documentation.

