## 9.6 Primary Endpoint Analyses

Primary endpoint analysis will be done on the level of the sub-study. A detailed description of the statistical analysis will be specified in the sub-study documentation.

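### Does the misconduct clause in section 13 let fraudulent data into the results because it names only an undefined per-protocol group?

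*Combined protocol and SAP*

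**What the plan says.** Section 13 sets the trigger: "Gross misconduct on behalf of an Investigator, such as intentional non-compliance with CIP or GCP requirements or fraud, will result in disqualification". The sanction can fall on the investigator, the site or both. The consequence for the data is one sentence: "Data provided by the Principal Investigator or Investigational Site will be excluded from the per-protocol analysis group". No other analysis set is mentioned.

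Section 9.5, headed Analysis Populations, names no population. It reads in full: "A detailed description of the statistical analysis that will be used for each sub-study will be described in the sub-study documentation". Section 9.1 states "Data will be analysed separately per sub-study", and section 9.6 states "Primary endpoint analysis will be done on the level of the sub-study". Section 4.1 adds that every sub-study is submitted separately with its own CIP and ends in its own report.

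Two other passages bear on the point. In section 7.3, external investigators recruit, obtain consent and check eligibility, after which "Subjects may then be referred to the sponsor principal investigator of internal (Cochlear) sites, who will conduct the remaining study procedures". Section 7.6, on the sponsor's role in conducting procedures, says "There is no mitigation for potential bias to the data integrity", and then says that sub-studies will be blinded when that can be done.

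**The concern.** A data-exclusion rule should say which data leave which analysis. Here the only set named has no definition in the plan, and the rule is stated outright at umbrella level, whereas most statistical matters are passed to the sub-study.

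Three difficulties seem to follow:

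- A sub-study whose main analysis uses all subjects could keep fabricated scores without breaching section 13.
- A sub-study without a per-protocol set would exclude nothing.
- One subject can be enrolled by one party and measured by another, so it is unclear whose data are removed if the enrolling investigator is disqualified.

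The stakes would be highest in a small sub-study. The synopsis plans 5 sites and analysis is per sub-study, so one site could supply much of the data, or all of it. The analysis is done at the sponsor, which also runs internal sites. If nothing were settled beforehand, the sponsor might decide whether the scores count after seeing them.

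**Working it through.** The plan states no figure on this point, so the check is mainly a reading of the text.

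**1. Is the group defined in the umbrella plan?** No. It is absent from the abbreviations (section 1). Section 7.2.5 defines subject statuses (enrolled, screen fail, participated, withdrawn), none of which is a per-protocol set. Sections 9.5 to 9.9 name no set. Section 17 allows a site to be discontinued for major non-adherence but does not mention its data. Section 13 is the only place where the term occurs.

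**2. Is it therefore undefined in the trial?** That cannot be concluded. Sections 4.1, 9.1, 9.5 and 9.6 send the analysis to sub-study documents that were not supplied. Those may define the per-protocol set and any other set.

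**3. What happens if section 13 is followed as written?**

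| Sub-study CIP | Effect of section 13 | Still open |
|---|---|---|
| Defines a per-protocol set | Data leave that set | Treatment in other sets, which the sub-study CIP can state |
| Defines no per-protocol set | Literally nothing is removed, although the intent to exclude is plain | Treatment in the sets it does use |

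In neither case does section 13 direct that the data be kept. Silence about the other sets leaves the matter to the sub-study. No umbrella-level estimate exists that the clause could make wrong: section 9.3.1 states no primary hypothesis and section 7.2.3 no power calculation.

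The trigger also covers two different situations. Fabricated scores are not measurements and belong in no performance analysis. Scores obtained under intentional non-compliance may be real measurements, and removing them from a per-protocol set is the usual convention. Treatment set by set is therefore reasonably settled where the sets are defined.

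**4. Can the data be attributed?** Largely. Section 7.3 sets out four arrangements and names the responsible principal investigator in each. Under section 14 each principal investigator confirms by electronic signature the data for subjects at that site. Scores taken by an internal site are thus that site's data. What remains is whether misconduct in consent or eligibility taints scores properly taken later by someone else. That is a narrow question, and it depends on the facts of the case.

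**5. Does section 7.6 raise the stakes?** Not for this point. The sentence concerns the sponsor carrying out procedures, and blinding follows it. Controls relevant to misconduct are elsewhere: monitoring (22.1), access to records for audit (22.2), audit trail and consistency checks (14), and site discontinuation (17).

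**6. How large could the effect be?** The documents give no sub-study size, standard deviation or shift, so every input here is an assumption: n = 20 subjects, paired SD 10 points, k affected subjects, each with a paired difference shifted by d.

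- Bias if the data are kept = (k/n) × d. For k = 4: 4/20 × 5 = 1.0 point, or 4/20 × 10 = 2.0 points. For k = 10: 10/20 × 5 = 2.5 points, or 10/20 × 10 = 5.0 points.
- Standard error = SD/√n. With all 20: 10/√20 = 2.24. After removing 4: 10/√16 = 2.50, up 12%. After removing 10: 10/√10 = 3.16, up 41%.

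The shift has to favour one condition. Each subject is their own control (section 7.3), so a shift d common to both conditions cancels: (A + d) − (B + d) = A − B. False-positive rates are not given, because the umbrella plan specifies no test to which they would apply.

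**The case for a change.** The strongest case for a change is that section 13 is a firm rule, and deferral elsewhere does not complete it. Section 9.5 defers the analysis without obliging each sub-study to define a per-protocol set, so the rule may have nothing to act on. Results guide the choice of product features (section 7.1.1), and some sub-studies may test non-inferiority or superiority, so feasibility status does not make every error harmless. Different wording would take a few sentences.

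It stands that the term is undefined here and that the plan is silent on other sets. It does not follow that tainted scores would be reported as results, or that the decision would have to be made after seeing them. Both assume that the sub-study CIPs are silent and that the analysts act unreasonably.

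A rewrite also carries its own risk. Limiting the exclusion to data found fraudulent or unverifiable would replace a blanket rule for the disqualified investigator or site with a case-by-case judgement after the event, which is the discretion complained of.

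Replacement of withdrawn subjects (section 7.2.6: "Participating subjects who are withdrawn/discontinued might be replaced. This will be specified in the sub-study documentation") is sometimes raised alongside this. It is expressly left to the sub-study and has nothing to do with misconduct.

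**Conclusion.** No change to the plan is needed. Section 13 uses a term that the umbrella CIP does not define and leaves other analysis sets unmentioned. This is missing detail in a clause that operates only after gross misconduct. The analysis sets belong in the sub-study CIPs, and an analyst would fill the gap sensibly by keeping fabricated scores out of every performance result and stating the exclusion in the sub-study report. Adverse events remain in the listings under section 9.9.

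The size cannot be established from the documents. The 1.0 to 5.0 point biases above rest wholly on assumed inputs and arise only if misconduct occurs, favours one condition, and the data are kept. The conclusion rests on the sub-study CIPs doing what section 9 assigns to them. Those CIPs were not available, so this could not be checked.
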